7.1.5.2. Incomplete Dates

If an AE onset date is incomplete or completely missing, the following rules will be used to determine if the AE is considered treatment emergent during the double-blind and open-label phases:

Events with Missing Onset Day and/or Month

The event is treatment-emergent during the double-blind phase if the following criteria are met:

- The month and year (or year) of onset date is the same as or after the month and year (or year) of the first dose of the blinded study drug, and
- For those who discontinued the blinded study drug permanently only: the month and year (or year) of onset date is the same as or before the month and year (or year) of the date of the minimum of the blinded study drug stop date + 3 days and the first dose date of open-label study drug, if applicable, and
- End date is as follows:
 - The (complete) end date is on or after the first dose date of the blinded study drug, or
 - The month and year (or year) of end date is the same or after the month and year (or year) of the first dose of the blinded study drug, or
 - End date is completely missing

The event is treatment-emergent during the open-label phase if the following criteria are met:

- The month and year (or year) of onset date is the same as or after the month and year (or year) of the first dose of the open-label study drug, and
- For those who discontinued the blinded study drug permanently only: the month and year (or year) of onset date is the same as or before the month and year (or year) of the date of the last dose of the open-label study drug + 3 days, and
- End date is as follows:
 - The (complete) end date is on or after the first dose date of the open-label study drug, or
 - The month and year (or year) of end date is the same or after the month and year (or year) of the first dose of the open-label study drug, or
 - End date is completely missing

Events with Completely Missing Onset Date

An AE with a completely missing onset date is defined as treatment-emergent AE during the double-blind phase if end date is as follows:

- The (complete) end date is on or after the first dose date of the blinded study drug, or
- The month and year (or year) of end date is the same or after the month and year (or year) of the first dose of the blinded study drug, or
- End date is completely missing

An AE with a completely missing onset date is defined as treatment-emergent AE during the open-label phase if end date is as follows:

- The (complete) end date is on or after the first dose date of the open-label study drug, or
- The month and year (or year) of end date is the same or after the month and year (or year) of the first dose of the open-label study drug, or
- End date is completely missing

7.1.6. Summaries of AEs and Deaths

For the Week 48 analysis, the treatment-emergent AEs occurring during the double-blind phase will be summarized based on the Safety Analysis Set.

A brief summary of AEs (ie, the number and percentage of subjects) will be presented by treatment group for the double-blind phase for the following: (1) any treatment-emergent AE, (2) any Grade 3 or 4 treatment-emergent AE, (3) any Grade 2, 3, or 4 treatment-emergent AE, (4) any treatment-emergent AE related to study drug, (5) any Grade 3 or 4 treatment-emergent AE related to study drug, (6) any Grade 2, 3, or 4 treatment-emergent AE related to study drug, (7) any treatment-emergent SAE, (8) any treatment-emergent SAE related to study drug, (9) any treatment-emergent AE leading to premature discontinuation of study drug, (10) any treatment-emergent AE leading to temporary study drug interruption, and (11) any death.

Treatment-emergent death occurring during the double-blind phase refers to death that occurs between the first dose date of blinded study drug to the minimum of the last dose date of blinded study drug + 3 days and the first dose date of open-label study drug, if applicable, for those who discontinued blinded study drug permanently. Treatment-emergent death occurring during the open-label phase refers to death that occurs between the first dose date of open-label study drug to the last dose date of open-label study drug + 3 days.

Summaries (number and percentage of subjects) of AEs (by SOC, HLT [if specified below], and PT) will be provided by treatment group and overall using the Safety Analysis Set for the double-blind phase as follows:

- All treatment-emergent AEs summarized by SOC, HLT, and PT
- Any Grade 3 or 4 treatment-emergent AEs
- Any Grade 2, 3, or 4 treatment-emergent AEs
- All treatment-emergent nonserious AEs occurring in at least 5% of subjects in any treatment group (this summary is generated per requirement for reporting in ClinicalTrials.gov)
- All treatment-emergent treatment-related AE summarized by SOC, HLT, and PT
- Any Grade 3 or 4 treatment-emergent treatment-related AEs
- Any Grade 2, 3, or 4 treatment-emergent treatment-related AEs
- All treatment-emergent SAEs
- All treatment-emergent treatment-related SAEs
- All treatment-emergent AEs leading to premature discontinuation from study drug
- All treatment-emergent AEs leading to temporary interruption of study drug

Multiple events will be counted once only per subject in each summary. For data presentation, SOC (and HLT) will be ordered alphabetically, with PT sorted by decreasing total frequency. For summaries by severity grade, the most severe event will be selected.

In addition to the by-treatment summaries, data listings will be provided for the following:

- All AEs
- Grade 3 and 4 AEs
- SAEs
- Treatment-related SAEs
- Deaths
- AEs leading to premature discontinuation of study drug
- AEs leading to temporary interruption of study drug

7.2. Laboratory Evaluations

For the Week 48 analysis, summaries of laboratory data will be provided for the double-blind phase based on the Safety Analysis Set. Analysis will be based on values reported in conventional units.

7.2.1. Summaries of Numeric Laboratory Results

Descriptive statistics (sample size, mean, SD, median, Q1, Q3, minimum, and maximum) will be provided by treatment group for each laboratory test specified in the study protocol as follows:

- Baseline values
- Values at each postbaseline analysis window
- Change from baseline to each postbaseline analysis window

In the case of multiple values in an analysis window, data will be selected for analysis as described in Section 3.8.3.

7.2.2. Graded Laboratory Values

The criteria specified in the protocol will be used to grade laboratory results as Grade 0, Grade 1 (mild), Grade 2 (moderate), Grade 3 (severe), or Grade 4 (life-threatening). Grade 0 includes all values that do not meet criteria for an abnormality of at least Grade 1. Some laboratory tests have criteria for both increased and decreased levels; analysis for each direction (ie, increased, decreased) will be presented separately.

If any laboratory toxicity grading scale overlaps with normal reference ranges (eg, Grade 1 scale overlaps with normal reference ranges), laboratory values within normal range will not be graded except for lipid tests.

7.2.2.1. Treatment-Emergent Laboratory Abnormalities

Treatment-emergent laboratory abnormalities occurring in the double-blind phase are defined as values that increase by at least 1 toxicity grade from baseline at any postbaseline visit up to and including the minimum of the blinded study drug stop date + 3 days and the first dose date of open-label study drug, if applicable, for those who discontinued blinded study drug permanently, or values that increase by at least 1 toxicity grade from baseline at any post-baseline visit for those who are still on blinded study drug. If the relevant baseline laboratory value is missing, any laboratory abnormality of at least Grade 1 observed within the double-blind time frame specified above will be considered treatment emergent.

Treatment-emergent laboratory abnormalities occurring in the open-label phase are defined as values that increase by at least 1 toxicity grade from open-label baseline at any open-label postbaseline visit up to and including the last dose date of the open-label study drug + 3 days for those who discontinued open-label study drug permanently, or values that increase by at least 1 toxicity grade from open-label baseline at any open-label post-baseline visit for those who are still on open-label study drug. For the analyses of abnormalities occurring during open-label treatment, open-label baseline will be considered to be the last available record on or prior to Open-Label Study Drug 1.

7.2.2.2. Treatment-Emergent Marked Laboratory Abnormalities

Treatment-emergent marked laboratory abnormalities occurring in the double-blind phase are defined as values that worsen by at least 3 grades from baseline at any postbaseline visit up to and including the minimum of the blinded study drug stop date + 3 days and the first dose date of open-label study drug, if applicable, for those who discontinued blinded study drug permanently, or values that worsen by at least 3 grades from baseline at any postbaseline visit for those who are still on blinded study drug. If relevant baseline laboratory data are missing, any laboratory abnormalities of at least Grade 3 or 4 observed within the double-blind time frame specified above will be considered as treatment-emergent marked laboratory abnormalities.

Treatment-emergent marked laboratory abnormalities occurring in the open-label phase are defined as values that worsen by at least 3 grades from open-label baseline at any open-label postbaseline visit up to and including the date of the last dose of open-label study drug + 3 day for those who discontinued open-label study drug permanently, or values that worsen by at least 3 grades from open-label baseline at any open-label postbaseline visit for those who are still on open-label study drug.

7.2.2.3. Summaries of Laboratory Abnormalities

The following summaries (number and percentage of subjects) of laboratory abnormalities will be provided by treatment group (subjects categorized according to most severe abnormality grade) during the double-blind phase:

- Treatment-emergent laboratory abnormalities
- Treatment-emergent Grade 3 and 4 laboratory abnormalities
- Treatment-emergent marked laboratory abnormalities

For all summaries of laboratory abnormalities, the denominator is the number of subjects with any nonmissing postbaseline value in the given study period. A listing of treatment-emergent Grade 3 or 4 laboratory abnormalities will be provided.

7.2.3. ALT Flare and Exacerbation of Hepatitis

Summaries of the incidence of ALT flare and exacerbation of hepatitis will be provided by treatment group using the subjects in the Safety Analysis Set for on-treatment occurrences during the double-blind phase and off-treatment occurrences. On-treatment occurrences in the double-blind phase will be defined as occurrences in the period between the first dose of blinded study drug to the minimum of the last dose date of blinded study drug + 3 days and first dose date of open-label study drug, if applicable, for those who discontinued blinded study drug permanently. Off-treatment occurrences will be defined as occurrences after the last dose of study drug + 3 days. A supportive listing will also be generated.

Incidence of ALT flare and exacerbation of hepatitis is defined as:

- Serum ALT $> 2 \times$ study baseline and $> 10 \times$ ULN, with or without associated symptoms

OR

- Confirmed ALT elevation (defined as 1 grade shift [ie, increase] or $2 \times$ previous value) with confirmed changes outside of the normal range in other laboratory parameters suggestive of worsening hepatic function (abnormal prothrombin time ≥ 2 seconds over study baseline or international normalized ratio [INR] ≥ 0.5 over study baseline, and abnormal serum albumin ≥ 1 g/dL below study baseline or elevated serum lactate levels [if available], defined as $2 \times$ ULN).

If the first of two consecutive results is in the double-blind phase and the second is out of the double-blind phase (ie, in the open-label or TFFU phase), then the result will be considered to be confirmed in the double-blind phase (assuming both values meet the criterion). And if the criterion is met by the last value in the double-blind phase, and no assessments are available after due to the subject exiting the study or data not yet available (eg, due to the data-cut), then the result will also be considered to be confirmed.

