3.1.2. Safety Analysis Set

The Safety Analysis Set will include all randomized subjects who have received at least 1 dose of study drug. Subjects will be analyzed according to the treatment they actually received during the double-blind phase. The actual treatment received will differ from the randomized treatment only when their actual treatment differs from randomized treatment for the entire double-blind treatment duration. This is the primary analysis set for safety analyses.

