3.2. Subject Grouping

For analyses based on the Full Analysis Set including the Serologically Evaluable Full Analysis Sets, subjects will be grouped according to the treatment to which they were randomized. For analyses based on the Per Protocol Analysis Set, Safety Analysis Set, Spine DXA Analysis Set, Whole Body DXA Analysis Set, subjects will be grouped according to the actual treatment received during the double-blind phase. The actual treatment received will differ from the randomized treatment only when their actual treatment differs from randomized treatment for the entire double-blind treatment duration.

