For subjects who completed blinded study drug and entered the open-label phase, the **Last Dose Date** is the latest non-missing end date of open-label study drug, recorded on the Study Drug Administration eCRF form with “Study Drug Permanently Discontinued” box checked for subjects who prematurely discontinued open-label study drug or who completed open-label study drug according to Open-Label Study Drug Completion eCRF. If the last dose date is missing (eg, due to lost to follow up) for subjects who prematurely discontinued open-label study drug, or for subjects who are still on open-label study drug, the latest of nonmissing open-label study drug start dates and end dates, the clinical visit dates, and the laboratory visit dates, excluding the dates during 24-week treatment-free follow-up, will be used to impute the last dose date.

Last Study Date is the latest of nonmissing study drug (blinded or open-label) start dates and end dates, the clinical visit dates, and the laboratory visit dates, including the 24-week treatment-free follow-up visit date, for subjects who prematurely discontinued study or who completed study according to Study Completion eCRF.

Baseline value for the double-blind phase is defined as the last nonmissing value obtained on or prior to Study Day 1.

Baseline value for the open-label phase is defined as the last nonmissing value obtained on or prior to Open-label Study Day 1.

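### SAP 7.2.3 tabulates off-treatment hepatitis flares by double-blind drug, so a flare after stopping open-label TDF in a placebo-arm child appears under Placebo; the off-treatment denominator is also not stated

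*SAP*

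**What the plan says.** SAP 7.2.3 covers two periods in one sentence. Incidence "will be provided by treatment group using the subjects in the Safety Analysis Set for on-treatment occurrences during the double-blind phase and off-treatment occurrences". The on-treatment window is tied to blinded study drug. The off-treatment window is tied to study drug without that qualifier: "Off-treatment occurrences will be defined as occurrences after the last dose of study drug + 3 days".

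The treatment group comes from the general rules. SAP 3.1.2, on the Safety Analysis Set: "Subjects will be analyzed according to the treatment they actually received during the double-blind phase". SAP 3.2 repeats this: for that set, "subjects will be grouped according to the actual treatment received during the double-blind phase". The group differs from the randomised arm only if the wrong drug was taken for the whole double-blind phase.

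For children who completed blinded drug and entered the open-label phase, SAP 3.8.1 says that the Last Dose Date "is the latest non-missing end date of open-label study drug". SAP 3.8.2 starts the treatment-free follow-up phase more than 3 days after that date.

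On denominators, SAP 7.2.2.3 says that for all summaries of laboratory abnormalities "the denominator is the number of subjects with any nonmissing postbaseline value in the given study period". Section 7.2.3 neither repeats nor cites this rule.

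**The concern.** Under the current protocol, children in both arms are to switch to open-label TDF after the blinded phase. An off-treatment flare in a child who made the switch follows withdrawal of TDF, whichever arm the child came from. A table headed by the double-blind drug does not show this. It can place a post-TDF event in the Placebo column beside events that really did follow placebo.

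The protocol treats this event as important. Sections 6.3.1 and 7.6.6 warn of exacerbation and decompensation when drug is stopped in children with bridging fibrosis or cirrhosis, and section 7.3 makes the flare criteria reportable as SAEs. With 89 treated children, one event in the wrong column changes how the table reads.

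The denominator is a second, smaller matter. Only children who have stopped drug can have an off-treatment event. A percentage over all treated children answers a different question from the risk among those who stopped.

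**Working it through.** Section 7.2.3 states no figure to reproduce, so the check traces the definitions and then illustrates the size.

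**Step 1: column against drug withdrawn.** The column comes from SAP 3.1.2 and 3.2, the drug withdrawn from SAP 3.8.1.

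| Path of the child | Drug withdrawn before the flare | Column in the 7.2.3 table |
|---|---|---|
| Placebo, stops in the blinded phase | Placebo | Placebo |
| Placebo, then open-label TDF, then stops | TDF | **Placebo** |
| TDF, stops in the blinded phase | TDF | TDF |
| TDF, then open-label TDF, then stops | TDF | TDF |

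The second row is the defect. No section of the SAP regroups an off-treatment event by the last drug taken.

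**Step 2: does another rule remove these events?** The opening of SAP section 7 limits safety summaries to the double-blind phase unless otherwise specified. Section 7.2.3 does specify otherwise, because it names off-treatment occurrences as a separate category.

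**Step 3: who can have an off-treatment event?** For a child still on open-label drug, SAP 3.8.1 imputes the Last Dose Date as the latest dosing, clinic or laboratory date outside follow-up. Such a child has no laboratory value after Last Dose Date + 3 days and cannot contribute an event.

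**Step 4: two possible denominators.**
- Whole Safety Analysis Set: rate = events / number in arm. Children still on drug are counted.
- Study-period rule of 7.2.2.3: rate = events / children with a value in the off-treatment period. There is then little or no dilution.

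Naming the Safety Analysis Set does not decide between them. The opening of SAP 7.2 names the same set for the laboratory summaries to which the 7.2.2.3 rule applies.

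**Step 5: illustration.** Documented inputs are 89 treated (SAP 1.3) and 2:1 allocation (SAP 1.2). At 2:1, 89 × 2/3 = 59.3 and 89 × 1/3 = 29.7; 60 TDF and 29 placebo is assumed. The numbers who stopped are not in the documents; 3, 6 and 12 per arm are assumed.

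*Attribution.* One placebo-arm child flares after stopping open-label TDF. The table reads Placebo 1/29 = 3.4%, TDF 0/60 = 0%. By last drug taken, the same data show one event after open-label TDF and none after blinded placebo.

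*Denominator.* One off-treatment flare in an arm:

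| Assumed number who stopped | Among those who stopped | Over 60 TDF | Over 29 placebo |
|---|---|---|---|
| 3 | 1/3 = 33.3% | 1/60 = 1.7% | 1/29 = 3.4% |
| 6 | 1/6 = 16.7% | 1.7% | 3.4% |
| 12 | 1/12 = 8.3% | 1.7% | 3.4% |

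The ratio of the whole-set rate to the rate among those who stopped is (number stopped) / (number in arm). This gives 3/60 = 0.05 to 12/60 = 0.20 for TDF, and 3/29 = 0.10 to 12/29 = 0.41 for placebo. It applies only if the whole set is the denominator.

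**The case against.** The best case for leaving the text alone is that the table is descriptive and the planned output already lets a reader interpret it. Section 7.2.3 specifies no test or confidence interval. It has its own supportive listing, SAEs are listed by subject (SAP 7.1.6), and disposition separates stopping blinded drug, stopping open-label drug and entering follow-up (SAP 4.2). This SAP covers the Week 48 analysis; the protocol plans later analyses after Weeks 144 and 192, when stops after open-label TDF have had longer to occur. By the Week 48 data cut there may be few or none.

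Most of this stands as a limit on size. It does not correct the table: a reader would have to reassign cases by hand from a listing, while the summary still counts them under Placebo. The SAP defines adverse events, deaths and graded laboratory abnormalities separately for the double-blind and open-label phases (7.1.5.1, 7.1.6, 7.2.2.1, 7.2.2.2), so the same care here would be consistent with the rest of the plan.

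Four stronger readings are tempting but not supported:
- *That dilution is certain.* Section 7.2.2.3 may govern the denominator. It sits in a neighbouring subsection whose listed tables are for the double-blind phase, so its reach is unclear either way.
- *That study drug might mean blinded drug only, so that flares on open-label TDF count as off-treatment.* SAP 3.8.1 defines the last dose of blinded drug separately from the Last Dose Date, 3.8.2 uses the latter, and 7.2.3 itself changes its wording between the two windows.
- *That every child who completes blinded drug goes on to TDF.* SAP 3.8.1 provides for completers who do not enter the open-label phase.
- *That stops after open-label TDF are to be expected by the data cut.* The documents give no data-cut date and no counts of children who stopped.

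**Conclusion.** The attribution problem holds. It follows from SAP 3.1.2, 3.2, 3.8.1, 3.8.2 and 7.2.3 taken together and needs no assumed number. As written, the Placebo column of the off-treatment table can contain flares that followed withdrawal of TDF.

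The denominator is unspecified; it has not been shown to be wrong. The incidence is diluted only if the whole Safety Analysis Set is used.

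The size is unknown. The percentages rest on an assumed 60:29 split, assumed numbers who stopped and a single hypothetical event. They show how sensitive a small table is and do not predict a result. No hypothesis test, efficacy result or trial procedure is affected. The change is worth making before the analysis, because it removes a known misplacement in a safety table at little cost.

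**What to change.** In SAP 7.2.3:
- Present off-treatment occurrences by the last study drug taken before stopping: blinded placebo, blinded TDF or open-label TDF.
- State the denominator: children who stopped study drug and have at least one ALT after last dose + 3 days. Report n/N.
- Show the double-blind arm in the supportive listing, so that both views are available.

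No extra exclusion for later anti-HBV therapy seems needed, because SAP 1.2 already ends follow-up when active treatment starts.

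The cost is a short wording change and one revised table shell. Dose dates and phases are already derived under SAP 3.8.1, so no new data or test is needed. The downside is small denominators, which is why n/N is preferable to a percentage alone.
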